### 4.2 Circulating Biomarkers

Inflammation is thought to play an important role in HIE and CP. Biomarkers of inflammation that we measure include: interleukin (IL)-1 $\beta$ , IL-6 and IL-8 and TNF- $\alpha$ . Putative biomarkers of brain injury in neonatal HIE include: glial fibrillary acidic protein (GFAP), ubiquitin C-terminal hydrolase-L1 (UCH-L1), S100B, Tau, and neuron-specific enolase (NSE).

### 4.3 Neuroimaging Outcomes

The HEAL neuroimaging outcome measure is the total MRI injury score based on a previously validated MRI scoring system for HIE. This score indicates the extent of signal abnormality (i.e., 0=none, 1 $\leq$ 25%, 2=25%–50%, 3 $\geq$ 50%) for each of the deep grey nuclei, PLIC, cerebral cortex, white matter and cerebellum, as well as brainstem (scored on a 0–2 scale) separately for each sequence. ‘Signal abnormality’ is defined qualitatively as either abnormally low or high signal on T1w and T2w images or areas of restricted diffusion on Trace-weighted or ADC images calculated from the DTI sequence. We do not employ a quantitative threshold for ADC, consistent with the previously validated scoring system. Areas with high ADC are not scored as injury for the DTI images, which is designed to measure acute injury; however, correspondent areas of low and/or high signal on the T1w and/or T2w images are scored.

For each ROI, injury is scored qualitatively for each sequence on a 4-point scale based on the extent of signal abnormality (0=none, 1 $=$ <25%, 2=25%–50%, 3 $\geq$ 50%), except for the brainstem which is scored on a 3-point scale (0=none; 1=focal; 2=multifocal/widespread).

To compute the MRI injury score, each scan is reviewed independently by two of three experienced readers ([name], [name], and [name]), who are blinded to the infant’s clinical course, treatment assignment and MRS findings. After the primary review, each scan undergoes final consensus review during which any discrepancies are reviewed by all three reviewers and resolved by consensus. The individual and consensus scores are then classified as none (total=0), mild (1–11), moderate (12–32) or severe (33–138), in accordance with the previously validated MRI injury classification. Inter-rater reliability between the three independent readers will be determined for both the total score and for the categorical classification (none, mild, moderate, severe). For the total score, we will use a general linear mixed effects model to estimate the intraclass correlation coefficient (ICC). For the categorical classification, we will use kappa.

Secondary MRI measures include the MRI injury severity classification discussed above as well as classification of injury pattern and acuity. Injury pattern is classified as: (1) normal MRI (defined as no evidence of injury); (2) central (injury to the BGT $\pm$ perirolandic cortex); (3) peripheral (injury to the parasagittal cortex and/or WM, i.e, ‘borderzone/watershed distribution’); (4) global (injury to BGT+ total or near total involvement of cortex $\pm$ underlying WM); (5) punctate WM Lesions (discrete foci of injury typically 1–10 mm in size localised to the periventricular WM or centrum semiovale); (6) arterial ischaemic stroke (infarct localised to the vascular territory of the middle, anterior or posterior cerebral arteries); (7) other focal lesions (includes venous infarcts, contusions, and unilateral lesions to the BGT,

cortex or white matter not classified elsewhere) and (8) atypical/not otherwise specified (with additional text field for describing the lesion). The scoring system allows for multiple patterns to be coded, which will allow us to determine the frequency of individual patterns as well as the co-occurrence across patterns.

#### **4.4 Hearing and Cortical Visual Impairment**

To explore the effect of Epo on sensory deficits that can result from HIE, we will collect 2-year data regarding hearing impairment requiring hearing aids, and if available, information about the presence of cortical visual impairment diagnosed by an ophthalmologist.

### **5. Data Analyses**

#### **5.1 Primary Outcome**

The primary analysis will be a test of equality of the rate of the primary outcome (death or neurodevelopmental impairment (NDI)) across the two randomized investigational groups. Specifically, we will use a likelihood ratio test based on logistic regression, with stratification by recruitment center and HIE severity. We will perform modified Intention to Treat (mITT) analysis and expect minimal non-compliance due to the nature of the intervention in relation to in-patient care. For the primary endpoint, we expect uniform and complete ascertainment of death but may not evaluate all subjects for developmental impairment. We plan to perform a primary analysis based on complete cases and will exclude those subjects for whom vital status is known (alive) but NDI cannot be assessed. Sensitivity analysis will use multiple imputation to evaluate the potential impact of any missing data. Secondary analysis will consider an ordered categorical two-year status measure (death/severe or moderate impairment/mild impairment/normal), and analysis will be based on generalized Wilcoxon tests.

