6.3.2 Clinical assessment

Each of the clinical characteristics listed below will be recorded on the Case Report Forms (CRFs) at the time points indicated.

6.3.2.1 Screening clinical assessment (<24+2 hours):

1. Apgar scores at 5 and 10 minutes

2. Resuscitation: presence of endotracheal ventilation, mask ventilation, CPAP, or chest compressions at 10 minutes after delivery.
3. Acidosis: pH and base deficit in a cord, arterial, or venous blood sample taken before 60 minutes of age.
4. Sarnat Exam Procedures. The modified Sarnat Exam should be performed between 1-6 hours of age prior to administering sedative medications, by a neonatologist, neurologist, pediatrician or neonatal nurse practitioner. The qualifying Sarnat exam should be the worst exam before sedative medications are administered to the infant. The exam cannot be evaluated in an infant who is under the influence of paralytic medications.

A Sarnat Screening Worksheet (1 page, hard copy) must be filled out for all enrolled infants. We will record the age of the infant (in hours) at the time of the qualifying exam.

The examiner should be trained in the HEAL Sarnat examination whenever possible. If the examiner has not undergone HEAL Sarnat training, the exam should be *confirmed* by a HEAL physician by 24 hours of age, by at least one of the following mechanisms: 1) The HEAL research physician performed the qualifying exam; 2) HEAL research physician discussed the findings with the outside physician/transport team member who performed the exam; or 3) HEAL research physician corroborated the exam findings with a treating physician who spoke with the Sarnat examiner.

The Sarnat Screening Sheet must be **signed by the HEAL Physician** who confirmed the exam. It is permissible for signature to occur after the subject has been enrolled, however, whenever possible, the Sarnat should be verbally confirmed prior to enrollment.

If the qualifying Sarnat exam is not done prior to receiving sedating medications, and/or cannot be confirmed by a HEAL physician by 24+2 hours of age, the infant could still qualify for the study. However, this will be noted on the Sarnat Screening Sheet. If a HEAL physician determines that an enrolled infant did not actually meet Sarnat criteria for eligibility, and the infant has already been enrolled, then this should be reported as a protocol violation.

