All items on the Sarnat Screening Sheet must also be entered into the HEAL Portal in order for the infant to be randomized and enrolled into the study.

The Sarnat Screening Sheet must be kept on file at each enrolling site, along with the infant's signed consent form. The Sarnat Screening Sheet will be used as a source document during monitoring visits, to ensure accuracy of data entry into the HEAL Portal.

5. Sarnat Exam Findings (Table 4).^{3,5,26} The HEAL study will incorporate a Modified Sarnat Exam to determine the degree of encephalopathy. "Severe" encephalopathy refers to the presence of more symptoms classified in the severe category than in the moderate category. If signs are equally distributed between the two categories, then designation of severity is based on level of consciousness.³ Degree of encephalopathy

will be calculated within the HEAL Portal, based on the exam findings that are entered into the screening form.

Table 4. Modified Sarnat Encephalopathy^{3,26}

Category	Normal	Mild Abnormality	Moderate Abnormality	Severe Abnormality	Unable to assess?
1. Level of consciousness	Normal	Hyperalert or irritable	Lethargic or poorly responsive	Minimal or no responsiveness	N/A
2. Spontaneous activity	Normal	Slightly decreased	Decreased	Absent	N/A
3. Posture	Normal	Mild distal flexion	Distal flexion, complete extension	Decerebrate	N/A
4. Tone	Normal	Hypertonic	Hypotonic	Flaccid	N/A
5. Primitive reflexes					
a. Suck	Normal	N/A	Weak or bite	Absent	Unable to assess
b. Moro	Normal	Low threshold to elicit	Weak or incomplete	Absent	Unable to assess
6. Autonomic					
a. Pupils	Normal	N/A	Constricted	Dilated and either fixed or sluggishly reactive; asymmetric	Unable to assess
b. Respiration	Normal	N/A	Periodic Breathing	Intubated and ventilated	N/A

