6.3.2.2 Demographics

Demographic information: maternal and paternal race and ethnicity; maternal education will be collected prior to discharge. Variables from the NINDS Common Data Elements will be used.

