9 STATISTICAL CONSIDERATIONS

9.1 GENERAL

This study is a randomized parallel group double-masked, placebo controlled trial in neonates with HIE. Eligible neonates will be enrolled and treated with either Epo or normal saline over 7 days and followed for a fixed period of 24 months (±56 days) for survival and neurological outcomes. The follow-up period was chosen to provide meaningful motor and cognitive outcomes, since CP and motor and cognitive

deficits are more reliably diagnosed at 2 years of age. Enrolled children will be randomized, stratified by study site and severity of HIE, with equal likelihood to receive Epo or saline.

Analyses will be based on a modified Intention to Treat (mITT) approach. In this approach, all randomized neonates who received at least one dose of study drug will be included in the analyses. Neonates whose parents withdrew consent after randomization and before the first dose will be excluded from the mITT. Since the first dose is within 24 hours of birth and within at most a few hours after consent and randomization, we do not expect more than a very small number of withdrawals.

Preliminary analyses will compare baseline characteristics to explore whether there are any imbalances that occurred at randomization. These analyses will include comparing demographics and the Sarnat score at study entry.

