## 3. Secondary Outcomes

At age 2, we will assess the effect of Epo on secondary outcomes: a) presence of CP, b) severity of motor impairment, c) Bayley III cognitive and language scores, d) epilepsy (i.e.,  $\geq 2$  afebrile, unprovoked seizures), and e) behavioral abnormalities (i.e., attention problems or aggressive behavior) based on the CBCL externalizing score.

Severity of motor impairment will be determined by type of CP and GMFCS level (**Table 1**).

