#### **5.2 Secondary Outcomes**

Generalized linear regression models will be used for binary and continuous secondary outcomes, adjusted for recruitment site and HIE severity.

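### The primary and Bayley/CBCL models are valid but adjust only for site and two-level HIE severity, forgoing a modest efficiency gain from baseline variables already collected

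*SAP*

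**What the plan says.** For the primary outcome, SAP 5.1 specifies a likelihood ratio test from logistic regression, "with stratification by recruitment center and HIE severity". Protocol 9.3.1 specifies the same test. For the secondary outcomes, SAP 5.2 states: "Generalized linear regression models will be used for binary and continuous secondary outcomes, adjusted for recruitment site and HIE severity". SAP 3 lists "Bayley III cognitive and language scores" and the CBCL externalizing score among those outcomes. Severity is the randomization factor, with two levels (SAP 1.3 and 5.5). Neither section names a further baseline covariate, a supportive model with more covariates, or a rule for missing covariates.

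The trial records more at baseline than these models use:

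- **Sarnat items.** Protocol Table 4 grades six categories (eight items) from normal to severe, and Protocol 6.3.2.1 requires entry: "All items on the Sarnat Screening Sheet must also be entered into the HEAL Portal in order for the infant to be randomized".
- **Apgar.** The screening assessment in the same section includes "Apgar scores at 5 and 10 minutes".
- **Maternal education.** Protocol 6.3.2.2 says that "maternal education will be collected prior to discharge"; Protocol 6.3.8.5 also lists it for follow-up.
- **Sex.** It is implied by the male/female subgroup analysis (SAP 5.1.1), although the demographics list does not name it.

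Protocol 9.1 uses some of these variables to check balance between arms: "These analyses will include comparing demographics and the Sarnat score at study entry". It does not say what follows if an imbalance is found.

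**The concern.** A baseline variable that predicts outcome beyond site and severity adds unexplained variation if it is left out. Prespecifying it usually raises power without new data. The two-level severity factor also discards detail by construction. Under Protocol 6.3.2.1 an infant is severe only when severe signs outnumber moderate ones, with level of consciousness breaking ties. An infant with no severe sign and an infant with two severe and three moderate signs are therefore both moderate.

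At stake is efficiency: somewhat lower power and wider intervals than the same infants could give. This matters most if the true effect is smaller than planned, and for the continuous Bayley score.

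**Working it through.** **1. The plan's own figure.** Inputs from SAP 7.1.4 and SAP Table 4: 225 evaluable per arm, control rate 49%, Epo rates 32–35%. Two-sided alpha 0.05 is stated in SAP 7.2 for the ordinal outcome and assumed here for the primary.

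The check is a two-proportion test with continuity correction. With d the difference in rates, n* = n(1 − 1/(nd))², and power = Φ[(d√n* − 1.96√(2p̄(1−p̄))) / √(p₁(1−p₁) + p₂(1−p₂))].

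At 33%: d = 0.16, n* = 225(1 − 1/36)² = 212.7, p̄ = 0.41. Power = Φ[(0.16 × 14.58 − 1.96 × 0.6956)/0.6863] = Φ(1.41) = 92.1%.

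| Epo rate | SAP Table 4 | Corrected formula | Fisher exact |
|---|---|---|---|
| 32% | 95% | 95.0% | 94.9% |
| 33% | 92% | 92.1% | 92.1% |
| 34% | 88% | 88.2% | 88.2% |
| 35% | 83% | 83.2% | 83.3% |

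All four rows reproduce with no covariate at all, so the stated power takes no credit even for site and severity.

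**2. Primary model with added covariates.** Logistic likelihood ratio tests were simulated for 450 infants at 17 sites (the number in the original proposal, SAP 7.5), blocked within site and severity, with 3,000 runs per cell. The following are assumptions, because the documents give none of them: 25% severe, severity odds ratio 5, site SD 0.3 on the logit scale, and four generic added covariates whose joint AUC runs from 0.50 (useless) to 0.72. Each cell shows power (%) with site and severity, then with the four covariates added.

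| Added AUC | Epo 33% | Epo 35% | Epo 37% |
|---|---|---|---|
| 0.50 | 95.4 → 95.1 | 90.7 → 90.8 | 79.7 → 79.8 |
| 0.60 | 95.8 → 96.5 | 89.5 → 90.3 | 80.2 → 80.9 |
| 0.66 | 96.0 → 97.3 | 89.8 → 92.1 | 79.5 → 83.4 |
| 0.72 | 95.7 → 97.7 | 89.3 → 93.4 | 78.8 → 85.1 |

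The simulation error of one power figure is √(p(1−p)/3000), or 0.4 points near 95% and 0.7 near 80%, so the small fall in the first cell is noise. Type I error was about 5–6% with and without the added covariates (1,500 runs per cell).

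**3. Bayley cognitive score.** The planning SDs are 11.7 and 15.2 (SAP 7.1.3), with root mean square √((11.7² + 15.2²)/2) = 13.6. Mortality of 14% (SAP 7.1) leaves 225 × 0.86 ≈ 194 per arm. The 4-point difference is chosen for illustration, and 13.6 is taken as the SD before the extra covariates.

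Power = Φ[4/(13.6√(1−R²)√(2/194)) − 1.96], and the sample-size equivalent is 1/(1−R²).

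| Extra R² (assumed) | Power | Difference detectable at 80% power | Equivalent sample size |
|---|---|---|---|
| 0 | 82.6% | 3.87 | 1.00 |
| 0.05 | 84.4% | 3.77 | 1.05 |
| 0.10 | 86.3% | 3.67 | 1.11 |
| 0.20 | 89.9% | 3.46 | 1.25 |

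No separate figure was computed for the CBCL score.

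**4. What a careless version would cost.** Suppose infants with a missing covariate were dropped. In the formula of step 1, 5% missing (213.8 per arm) lowers power from 92.1% to 90.7% at 33% and from 83.2% to 81.1% at 35%. With 10% missing (202.5 per arm) it falls to 89.0% and 78.9%. That could cancel the gain.

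**The case against.** The strongest reply is that nothing is wrong. Both models adjust for both stratification factors, the test is valid, and no section promises more. At the planned effect there is little room to gain: site and severity alone gave 95–96% simulated power, already above the stated 92%. All of this stands.

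Four further points limit the claim:

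- **Overlap.** The Sarnat count and the severity factor come from the same examination. With at least three of six criteria required and signs counted by category, moderate infants can have 0–3 severe categories and severe infants 2–6. Much of the information is already in the model, so the upper end of the range may be out of reach.
- **Missing values.** A reader might infer that Sarnat data are complete because entry is compulsory. Protocol Table 4 allows suck, Moro and pupils to be recorded as not assessable, so an entered item need not be a graded one. Completeness of the 10-minute Apgar is not documented; it is one of four alternative entry routes (Protocol 4.1). A simple rule handles both.
- **Timing.** Maternal education may be recorded after randomization. Masked study drug cannot plausibly change it, so this does not bar its use.
- **Estimand.** Extra covariates change the conditional odds ratio being estimated. The planned odds ratio is already conditional on site and severity, and the primary analysis is a test of equality, so this is a reporting matter.

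A reader might also infer that the gain is free, or that known prognostic variation is being wasted. The documents support neither. They report no association between these variables and outcome, and if the variables add nothing beyond severity the gain is nil. Nor are the variables unused altogether: sex enters the subgroup analysis and the Sarnat score the balance check.

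**Conclusion.** The point holds as a missed efficiency. The direction is well founded; the size is assumed. Over an added-covariate AUC of 0.50 to 0.72, with site and severity already in the model, the primary gain is about 0–2 points of power at 33%, 0–4 at 35% and 0–6 at 37%, the last lying beyond the plan's power table. For the Bayley score an extra R² of 0.05 to 0.20 is worth about 2–7 points at a 4-point difference. The simulation used generic covariates rather than the named ones, so it shows a plausible range and does not predict the result in this trial. The case is stronger for the Bayley score, and for effects smaller than planned, than for the primary test at its design effect. It should be labelled a cheap improvement.

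**What to change.** Before unmasking, amend the SAP as follows.

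- **SAP 5.1.** Add to the primary model the number of Sarnat categories scored severe (0–6), the 10-minute Apgar score and sex. A category counts as severe if any assessable sub-item is severe; unassessable sub-items are ignored. State the functional form of each term.
- **SAP 5.2.** Add sex and maternal education to the Bayley and CBCL models.
- **Missing covariates.** Use a missing indicator, or single imputation blind to arm and outcome, so that no infant is dropped.
- **Sensitivity.** Keep the site-and-severity model as a prespecified sensitivity analysis. If the sponsor prefers to leave the primary model unchanged, the adjusted primary model can be the supportive one, with the Bayley change still made.

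The cost is SAP wording and no new data. The downsides are a few more model terms (more with missing indicators), a slightly different conditional odds ratio, partial overlap of the Sarnat count with severity, and no gain if the covariates carry nothing beyond severity.

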9.3 DATA ANALYSES

9.3.1 Primary outcome analyses

The primary analysis will be a test of equality of the rate of the primary outcome (death or neurodevelopmental impairment (NDI)) across the two randomized investigational groups. Specifically, we will use a likelihood ratio test based on logistic regression, with stratification by recruitment center and HIE severity. We will perform Intention to Treat analysis and expect minimal non-compliance due to the nature of the intervention in relation to in-patient care. For

the primary endpoint, we expect uniform and complete ascertainment of death but may not evaluate all subjects for developmental impairment. We plan to perform a primary analysis based on complete cases and will exclude those subjects for whom vital status is known (alive) but NDI cannot be assessed. Sensitivity analysis will use multiple imputation to evaluate the potential impact of any missing data. Secondary analysis will consider an ordered categorical two-year status measure (death/severe or moderate impairment/mild impairment/normal), and analysis will be based on generalized Wilcoxon tests or regression models for ordered categorical outcomes such as the proportional odds model. Secondary quantitative measures include MRI-based injury score using the Washington University Standardized Scoring System. For these endpoints, a stratified t-test provides inference regarding the mean response across the treatment groups. We will adjust all secondary outcome analyses for recruitment site and HIE severity using regression methods.

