## 2.4 Adjudication of Primary Outcome

There may be cases of only a phone follow-up rather than an in-person visit, or otherwise partial data. The CCC will create an Outcomes Adjudication Committee, who will be masked to the treatment assignment of the child. The Committee will receive all available data on the long-term outcome of these toddlers and will assess whether they can definitively assign a primary outcome level and what it is, or they do not have sufficient information to make that determination and therefore the value will be imputed. This model was successfully previously used in the NO CLD clinical trial long-term outcome.

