## 6.3 Handling

In final manuscripts and analyses, the number of non-responders will be enumerated by study arm according to CONSORT guidelines. We will conduct a missing data analysis to describe and characterize enrolled participants who do not provide further response due to attrition or dropout. We will also conduct sensitivity analyses using 10-fold multiple imputation to assess the robustness of the results when missing data are imputed.

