## 6.4 Statistical Uncertainty

Given the type of missing data we expect in the proposed study, missing completely at random (MCAR) or missing at random (MAR), both methods we propose to utilize for missing data properly account for statistical uncertainty due to missingness and will provide accurate confidence interval coverage.

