## 6.5 Sensitivity Analysis

We will assess the sensitivity of inferences made from missing data methods first by using the two previously described methods for dealing with missing data, and secondly by imputing missing data under both pessimistic and optimistic scenarios to provide bounds on the statistical uncertainty. The

characteristics of non-responders will be summarized in our final report where we will present the sensitivity of the treatment effect due to missing data.

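### Does leaving the sensitivity imputation unspecified empty the check on the primary result?

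*SAP*

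**What the plan says.** SAP 5.1 states that "we expect uniform and complete ascertainment of death but may not evaluate all subjects for developmental impairment". It then describes a "primary analysis based on complete cases and will exclude those subjects for whom vital status is known (alive) but NDI cannot be assessed"; protocol 9.3.1 has the same rule. Next it says: "Sensitivity analysis will use multiple imputation to evaluate the potential impact of any missing data". SAP 6.3 supplies the only technical detail: "We will also conduct sensitivity analyses using 10-fold multiple imputation to assess the robustness of the results when missing data are imputed".

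Three other places bear on the point.

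- SAP 2.4 (and protocol 9.2.1.4) covers children with partial data. Where the masked committee cannot classify a child, "they do not have sufficient information to make that determination and therefore the value will be imputed".
- SAP 6.4 asserts that "both methods we propose to utilize for missing data properly account for statistical uncertainty due to missingness", and SAP 6.5 will examine sensitivity "first by using the two previously described methods for dealing with missing data". SAP section 6 describes multiple imputation only. Protocol 9.3.6.1 also has inverse probability weighting.
- SAP 6.5 adds best-case and worst-case imputations, without saying how the missing values are set in each arm.

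**The concern.** Deaths are expected to be fully known, so missing outcomes fall on survivors. At the planned loss, no deaths are missing but 25 of 215 control survivors are (11.6%). The composite is then not missing completely at random, and it is missing at random only given survival. A missing control child carries the survivors' NDI risk, 35/86 = 40.7%, not the composite risk of 49%.

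An analyst who imputed the composite from the primary model's own covariates would give these children roughly the composite risk and reproduce the complete-case answer. The planned robustness check would then show nothing. An unnamed target and unnamed predictors could also be chosen after the data are seen. Read literally, SAP 2.4 conflicts with the exclusion in SAP 5.1, and a reader of the SAP alone cannot find the second method.

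**Working it through.** **Inputs.** Control: death 14%, NDI 35%, composite 49% (SAP 7.1). Epo: composite 33% (SAP 7.1.4), with deaths at 14% (SAP Table 5, Scenario 1) or 12% (SAP 7.1.3 and Table 5, Scenario 2). 250 per arm, 225 evaluated (SAP 7.1.4). Two-sided 5% is stated for the four-level outcome in SAP 7.2 and assumed here for the primary test.

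**The plan's own figure.** Power = Φ[(|p1 − p2| − 1/n − 1.96·SE0)/SE1], with n = 225, p1 = 0.49, p2 = 0.33.

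- SE0 = √(2 × 0.41 × 0.59/225) = 0.0464
- SE1 = √[(0.49 × 0.51 + 0.33 × 0.67)/225] = 0.0458
- Power = Φ(1.41) = 92.1%

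SAP Table 4 states 92%. The same formula gives 95.0%, 88.2% and 83.2% for the other rows, against 95%, 88% and 83%. This power uses the evaluated number and does not involve imputation.

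**Complete cases against survivor imputation.** Suppose 25 survivors per arm are lost, unrelated to NDI. Complete-case rate = [deaths + (survivors − 25) × NDI rate in survivors]/225.

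| Arm | Calculation | Complete case | True |
|---|---|---|---|
| Control | (35 + 190 × 0.4070)/225 | 49.9% | 49.0% |
| Epo, 14% deaths | (35 + 190 × 0.2209)/225 | 34.2% | 33.0% |
| Epo, 12% deaths | (30 + 195 × 0.2386)/225 | 34.0% | 33.0% |

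The complete-case risk difference is 15.7 or 15.9 points. Imputing NDI among survivors recovers 16.0, a shift of 0.1 to 0.3. With no treatment effect and equal loss, both arms move to 49.9% and no spurious difference arises.

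**Does imputing the composite merely repeat complete cases?** I simulated 200,000 infants per arm. An assumed auxiliary measured in survivors had sensitivity 0.7 and specificity 0.8 for NDI. In the last column, assumed loss was 18% where the auxiliary was positive and 7.5% otherwise. Entries are control/Epo rates (%).

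| Method | Loss unrelated to NDI | Loss depends on the auxiliary |
|---|---|---|
| Full data | 48.8/33.1 | 49.1/33.0 |
| Complete case | 49.8/34.3 | 48.8/33.3 |
| Composite, arm only | 49.8/34.3 | 48.8/33.3 |
| NDI in survivors, arm only | 48.9/33.0 | 47.8/32.2 |
| Composite, with the auxiliary | 48.8/33.1 | 49.1/33.1 |

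The repetition is real when only arm is used. It remains nearly so (49.6/34.1) with an assumed baseline auxiliary recorded in every infant, including those who die. It disappears with information measured in survivors. Naming survivors as the target, without predictors, does not remove bias in the arm rates when loss depends on development.

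**The best-case and worst-case bounds.** With 12% Epo deaths, observed events over 250 are 44.9% and 30.6%. Setting all 25 missing to impaired gives 54.9% and 40.6%.

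- Opposite extremes by arm: 44.9 − 40.6 = 4.3 to 54.9 − 30.6 = 24.3 points.
- The same extreme in both arms: 54.9 − 40.6 = 14.3 and 44.9 − 30.6 = 14.3.

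The bounds are therefore very wide only under one reading, which SAP 6.5 does not state.

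**The case for a change.** The best case for a change is that a pre-specified check should be specified, and a few sentences would do it. Unequal loss strengthens it. With 10 control and 40 Epo survivors missing (an assumption; 14% deaths in both arms), complete cases give 49.3% − 35.1% = 14.3 points from unrounded rates, against 16.0. The reverse imbalance gives 17.1. With no true effect, the first pattern produces 50.6% against 49.3%, a spurious 1.2 points against Epo.

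What stands is that the target, predictors and scenarios are unwritten, that SAP 2.4 lacks a cross-reference, and that naming these would make the SAP tidier. But the bias under unequal loss belongs to the complete-case primary analysis, a choice the plan makes openly. The 1.2 points is about a quarter of the standard error, √(0.4935 × 0.5065/240 + 0.5058 × 0.4942/210) = 4.7 points.

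Nor is survivor imputation uniformly better. If children with NDI are lost half as often as other survivors, it gives 16.6 where complete cases give 16.3 to 16.4 and the truth is 16.0. If they are lost twice as often, it is slightly closer (15.6 to 15.7 against 15.4 to 15.6).

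**Conclusion.** No change is needed. The passages fit together on an ordinary reading. SAP 5.1 fixes the primary analysis as complete-case, so the imputation mentioned in SAP 2.4 can only belong to the sensitivity analysis. SAP 5.1 also names the missing quantity: NDI in children known to be alive. The missing-at-random statement in SAP 6.4 does not mention the composite and can hold for NDI among survivors. Useful predictors are already collected, namely WIDEA at 12, 18 and 24 months (protocol 6.2.3) and, for delayed visits, GMFCS by telephone (protocol 6.3.8). The reference to two methods looks like wording kept from protocol 9.3.6.1 after the weighting sentence was left out, and the protocol supplies the missing method.

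No stated rule or figure is shown to give a wrong result. At equal 10% loss unrelated to NDI, the choice of imputation moves the risk difference by 0.1 to 0.3 points. Simulated power with complete cases, composite imputation and survivor imputation was 92.6, 92.3 and 93.6% with 14% Epo deaths, and 92.9, 92.6 and 93.3% with 12%. Type I error was 5.4, 5.3 and 5.4%.

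This rests on the plan's event rates and on near-complete ascertainment of death. Markedly unequal loss would give the imputation more work to do, but would not alter the primary test as written.
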